Ethics Committee approval was obtained at all study centres before commencement of the trial, and all patients provided informed consent. All relevant factors were recorded on a trial case report form (CRF).

ERAS perioperative care principles were emphasised. All patients received prophylactic antibiotics according to established guidelines. Medications were mostly continued perioperatively unless or at the clinicians discretion, but we recommended withholding ACE-inhibitors and ARBs on the day of surgery. We recorded preoperative use of bowel preparation, fasting times, ERAS data, medications, and biochemistry and haematology results on the CRF. Choice of anaesthetic agents and perioperative analgesia were left to the discretion of the anaesthetist; such data were recorded.

The acceptable limits of low BP, and a definition of ‘hypotension’, vary widely.²⁹ We used a general guideline of systolic BP <90 mmHg for more than 5 mins, but also asked the attending anaesthetist to modify their acceptable lower limit of sBP at the commencement of surgery, and, according to randomly-assigned group, treat hypotension with additional IV fluid or vasopressor therapy. Such modifications to the acceptable lower sBP were recorded.

Patients were followed daily and outcomes were recorded until hospital discharge. We recommended that antihypertensive medications should be withheld until sBP was consistently at or above preoperative levels. Serum electrolytes, Hb/haematocrit, and a 12-lead ECG were ordered preoperatively and on Day 1 after surgery. CRP was measured on postoperative Day 3 and whenever sepsis was suspected. Additional laboratory tests were ordered if clinically indicated. On Day 3 all patients completed the 15-item quality of recovery score (QoR-15).³⁰

On Day 30 all patients were contacted by phone to ascertain if they have experienced any outcomes, and if detected, further testing was arranged. The QoR-15 was repeated on Day 30 along with World Health Organization Disability Assessment Schedule 2.0 (WHODAS), and the WHODAS was repeated at 3-, 6- and 12-month follow-up to ascertain survival status and new-onset disability.³¹

Outcomes

There is a need for patient-centered outcome assessments in the study of perioperative anaemia.^{32 25}

Primary Endpoint

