Persistent disability or death by 90 days, where persistent disability was defined as a WHODAS 2.0 score of at least 24 points (on the 48-point scale) at both 30 days and 90 days post-operatively,³¹ reflecting a disability level of at least 25% and being the threshold point between “disabled” and “not disabled” as per WHO guidelines.³³ Disability was assessed by the participant, but if unable then we used the proxy’s report.

Secondary Endpoints

Secondary endpoints include an *a priori* composite of 30-day mortality or major septic complications (sepsis, surgical site infection, anastomotic leak, and pneumonia), plus each individually, blood transfusion, acute kidney injury, ICU and hospital stay, unplanned admission to ICU, and quality of recovery (QoR-15).³⁰ We used the following definitions:

1. Death: all-cause mortality at 90 days, then up to 12 months after surgery
2. A composite (pooled) and individual septic complications: sepsis, surgical site infection, anastomotic leak, and pneumonia
3. Sepsis: using Centers for Disease Control and Prevention (CDC) with National Healthcare Safety Network (NHSN) criteria³⁴
4. Surgical site infection: using CDC criteria³⁴

5. Pneumonia: The presence of new and/or progressive pulmonary infiltrates on chest radiograph plus two or more of the following:
 - i. Fever $\geq 38.5^{\circ}\text{C}$ or postoperative hypothermia $<36^{\circ}\text{C}$
 - ii. Leucocytosis $\geq 12,000 \text{ WBC}/\text{mm}^3$ or leucopenia $< 4,000 \text{ WBC}/\text{mm}^3$
 - iii. Purulent sputum and/or
 - iv. New onset or worsening cough or dyspnoea.
6. Anastomotic leak: A defect of the intestinal wall at the anastomotic site (including suture and staple lines of neorectal reservoirs) leading to a communication between the intra- an extra luminal compartments.
7. Acute kidney injury: according to The Kidney Disease: Improving Global Outcomes (KDIGO) group criteria, but not urine output – for Stage 2 or worse AKI defined as at least 2-fold increase in creatinine, or estimated GFR decrease $>50\%$ ³⁵. We also plan to report renal replacement therapy up to 90 days after surgery
8. Unplanned admission to ICU within 30 days of surgery
9. Total ICU stay: additive, including initial ICU admission and readmission times up to Day 30
10. Hospital stay: additive, from the start (date, time) of surgery until actual hospital discharge , plus readmission(s) up to Day 30
11. Quality of recovery: QoR-15 score³⁰ on Days 3 and 30

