A cohort study comparing patients with and without postoperative anaemia, using prospective data collected in a large, pragmatic, multicentre, randomized trial, the RELIEF trial, in which patients were randomly assigned to either a restrictive (zero balance) or liberal IV fluid regimen, stratified by site and planned HDU/ICU admission.⁵ The intention-to-treat population of the RELIEF trial will be utilised, namely all participants who were enrolled, randomised and underwent induction of general anaesthesia for eligible surgery.

Inclusion and exclusion criteria are as for the RELIEF trial.⁵

GROUP AND ENDPOINT DEFINITIONS

ANAEMIA GROUP DEFINITION

Postoperative anaemia will be defined according to the World Health Organisation definition (males Hb <130 g/L, and female Hb <120 g/L), as measured on postoperative Day 3, using the “Lowest Haemoglobin concentration”. Patients with missing Day 3 haemoglobin data will have these values imputed rather than these patients being excluded (details below).

A secondary group definition will be studied defined as patients with severe anaemia (Hb <100 g/L) at day 3 postoperatively.

LIBERAL PERIOPERATIVE IV FLUID GROUP DEFINITION

Liberal and restrictive perioperative IV fluid groups are defined as the corresponding randomised arms of the RELIEF trial. In brief, Liberal protocol group received a bolus of Hartmann’s balanced salt crystalloid 10 ml/kg at the commencement of surgery followed by 8 ml/kg/h administered until the end of surgery, and then maintenance infusion continued at 1.5 ml/kg/h for at least 24 hours. Patients assigned to the Restrictive protocol group received approximately half of this IV fluid volume.⁵

ENDPOINT DEFINITIONS

Primary endpoint

Persistent disability or death by 90 days, where persistent disability was defined as a WHODAS 2.0 score of at least 24 points (on the 48-point scale) at both 30 days and 90 days post-operatively,³¹ reflecting a disability level of at least 25% and being the threshold point between “disabled” and

“not disabled” as per WHO guidelines.³³ Disability was assessed by the participant, but if unable then we used the proxy’s report.

Secondary endpoints

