IV fluids (total volume) will be tabulated according to reporting in the RELIEF trial, for intraoperative plus recovery room (combined), and Days 1, 2 and 3.

Daily weight and CRP (if done) on Day 3 will be reported as mean (SD).

STATISTICAL ANALYSES

All statistical analysis will be performed with the intention-to-treat population of the RELIEF trial.⁵

Descriptive statistics will be used to compare the baseline and pre-Day 3 characteristics of patients with and without post-operative anaemia on Day 3, hereafter titled 'anaemia groups'.

The binary primary outcome, persistent disability or death to 90 days, will be compared between anaemia groups using log-binomial regression to estimate risk ratios and 95% confidence intervals directly, adjusting for RELIEF randomised group, age, sex, ASA physical status, Charlson score, preoperative aspirin, haemoglobin (baseline), type of surgery, planned HDU/ICU (either), and duration of surgery. Should the log-binomial model fail to converge, modified Poisson regression with robust standard errors will be used. Methods for addressing missing Day 3 anaemia are provided below.

Other binary endpoints (#1-8, 12) will be analysed similarly. Duration of stay outcomes (#9,10) will be summarised using medians and interquartiles ranges, and compared across anaemia groups using parametric accelerated failure time models with adjustment for the same factors. QoR-15 scores (#11) will be summarised using medians and interquartiles ranges, and compared across anaemia groups using median regression with robust standard errors.

To assess the secondary aim, the risk of postoperative anaemia at Day 3 will be compared between RELIEF randomised arms using proportions and analysis using log binomial regression adjusted for planned ICU/HDU admission.

Baseline and pre-Day 3 characteristics of patients missing the Day 3 anaemia assessment will be compared with those who have the measurement present. If there is evidence of missing Day 3 anaemia being dependent on these characteristics then multiple imputation of Day 3 anaemia will be performed using chained equations, including baseline and post-baseline variables predictive of either Day 3 anaemia being missing or of Day 3 anaemia itself (defined by correlation ≥ 0.30 for either), including the relevant outcome variables in the imputation models.

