Exploratory subgroup analyses will be done for persistent disability or death to 90 days, acute kidney injury, Day 3 QoR-15, and hospital stay according to (i) RELIEF randomised group, (ii) the presence of preoperative anaemia, and (iii) receipt of a red cell transfusion. These will be reported as a web-supplement.

Secondary analyses of those with and without more marked anaemia (Hb <100 g/L) will be undertaken for the primary outcome (persistent disability or death to 90 days), plus Day 3 QoR-15 score and hospital re-admissions at 3 months.

REFERENCE

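### Does a WHODAS cut of 24 points on a 48-point scale contradict the 25% disability level stated for the primary endpoint?

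*SAP*

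**What the plan says.** The SAP (Endpoint Definitions, Primary endpoint) defines persistent disability as a "WHODAS 2.0 score of at least 24 points (on the 48-point scale) at both 30 days and 90 days post-operatively". It explains the cut as "reflecting a disability level of at least 25% and being the threshold point between" the disabled and the not disabled. The Protocol (Primary Endpoint) has the same cut, "WHODAS 2.0 score of at least 24 points (on the 48-point scale", and the same meaning, "reflecting a disability level of at least 25" per cent. The two documents do not differ on this point.

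The only other description of the instrument is in the Protocol, Study Procedures, which names the "World Health Organization Disability Assessment Schedule 2.0 (WHODAS), and the WHODAS was repeated at 3-, 6- and 12-month follow-up". It gives the visits but no scoring. Neither document states the number of items, the item coding, the lowest or highest possible score, or a formula that turns points into per cent. Both cite published sources for the instrument and the threshold. The SAP's citation numbers resolve only in the Protocol's reference list, because the SAP's own list has a single entry on another subject.

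**The concern.** Most readers take a score of 24 on a 48-point scale to be halfway up. On that reading the sentence contradicts itself: the points say 50% and the text says 25%.

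The cut decides which survivors count as events in the primary endpoint, so an error would travel. The SAP, Statistical Analyses, says: "The binary primary outcome, persistent disability or death to 90 days, will be compared between anaemia groups using log-binomial regression". The same outcome is used again where "Exploratory subgroup analyses will be done for persistent disability or death to 90 days" and where "Secondary analyses of those with and without more marked anaemia (Hb <100 g/L) will be undertaken for the primary outcome".

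If scores were held as 0 to 48 and the cut of 24 were applied to them, the endpoint would in effect require at least 50% disability. Survivors between 25% and just under 50% would be counted as free of disability. Deaths would be counted correctly either way.

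**Working it through.** **Inputs.** From the Primary Endpoint text in both documents: raw cut 24, a 48-point scale, stated level 25%. The minimum and maximum are not given, so they are treated as unknown.

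**Formula.** Per cent = 100 × (score − minimum)/(maximum − minimum).

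**Reproducing the stated 25%.** The printed inputs do not give it without an assumption about where the scale starts. The candidates are:

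| Assumed range | Per cent at 24 points | Points at 25% |
|---|---|---|
| 0 to 48 | 24/48 = 50.0% | 12 |
| 1 to 48 | 23/47 = 48.9% | 12.75 |
| 12 to 48 | 12/36 = 33.3% | 21 |
| 12 to 60 | 12/48 = 25.0% | 24 |
| 16 to 48 | 8/32 = 25.0% | 24 |

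**Solving for the minimum.**
- If 48 is the width: (24 − m)/48 = 0.25 gives m = 24 − 12 = 12, and the maximum is 12 + 48 = 60.
- If 48 is the maximum: (24 − m)/(48 − m) = 0.25 gives 24 − m = 12 − 0.25m, so m = 12/0.75 = 16. The width is then 32, which fits the description of a 48-point scale less well.

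On every range that agrees with the printed 25%, the raw cut is 24, as the plan states. A different raw cut is needed only on ranges that the printed 25% already contradicts.

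**What a mismatch would do.** Persistent disability requires the cut at both visits, so it depends on the lower of the Day 30 and Day 90 scores. With 0-to-48 storage and a cut of 24, the survivors affected are those whose lower score is 12 to 23, that is 12/48 = 25.0% to 23/48 = 47.9%. With 12-to-60 storage no one is affected. The number of patients cannot be computed for the first case, because the documents give no WHODAS distribution, disability rate or event rate. No sample-size or power figure depends on the cut.

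**The case for a change.** The strongest case for a change is that a SAP should let a reader derive the primary endpoint from its text, and here the reader must supply the scale's origin. The Protocol promised a more detailed plan, yet the SAP repeats its sentence without adding the scoring. Neither document says that a derived variable from the parent trial will be reused. An analyst could go wrong in either direction: by applying 24 to 0-to-48 scores, or by correcting the cut to 12 on 12-to-60 scores, where (12 − 12)/48 = 0% would make every survivor with both scores disabled. One sentence would remove the doubt.

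The omission stands: the range and the formula are not there, and a sentence giving them would be harmless. The rest is weaker.

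- The 50% appears only after adding a zero origin that neither document states. Figures that can all hold together are not in contradiction.
- The first error needs a storage format that the documents do not show. It also needs an analyst who overlooks the 25% printed in the same sentence, which is itself a check on the derivation.
- The second error departs from the plan, since both documents say 24 and nowhere propose 12.

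The documents do not prove the 12-to-60 range either. It is inferred from their own figures, on the assumption that 48 is a width.

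**Conclusion.** The concern does not call for a change. The plan gives the raw cut (24), its intended meaning (25%) and the timing, and gives them identically in both documents. What it leaves out is the origin of the scale, a detail that analysts fill in when they derive the variable. Under the reading that fits the printed figures with 48 as the width, the plan's cut is exactly 25% and the effect on the primary result is nil.

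This rests on two assumptions: that 48 is the width of the score, and that the RELIEF scores are stored on that same range. The second cannot be verified from the documents. It is settled by looking up the item coding of a dataset already collected, which is ordinary work in building the endpoint. The observed range alone might not settle it, because scores lying wholly within 12 to 48 would be compatible with both codings. Writing the range into the plan would record what the data dictionary already fixes. It would not alter the endpoint, the model or the interpretation.

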Association of Postoperative Anaemia with Patient Outcome in the RELIEF Trial

ClinicalTrials.gov Identifier: NCT04978285

Statistical Analysis Plan

28 September, 2021

BACKGROUND

Both preoperative anaemia and red cell transfusion are independent risk factors in major surgery. Patient blood management (PBM) aims to reduce the need for blood transfusion in an effort to improve patient outcomes. Australian PBM guidelines for the surgical patient are available, but there is no specific PBM guidance on the treatment of *postoperative* anaemia.

The consequences of *postoperative* anaemia remain unclear. Postoperative anaemia is more likely if there is pre-existing anaemia, but also increased perioperative blood loss, frequent blood sampling, excess IV fluids (leading to haemodilution), sepsis, and inadequate nutritional intake after surgery. A nadir in Hb concentration is most often observed within the first 3–4 days after surgery. Postoperative anaemia is believed to have deleterious effects on patient outcomes, including prolonged hospital stay, increased postoperative complications, and perhaps poor survival, but there is very little data to support this belief.

We therefore propose a study to investigate the incidence, extent, and outcomes of patients with anaemia after major surgery, including an assessment of the amount of IV fluids administered in the immediate perioperative period.

STUDY AIMS AND HYPOTHESES

Primary aim - To investigate the relationship between postoperative anaemia and patient-centred outcomes after major abdominal surgery.

Secondary aim – To determine whether a more liberal perioperative IV fluid strategy increases the risk of postoperative anaemia (haemodilution) at Day 3.

Hypothesis: Adults with anaemia in the immediate postoperative period following major abdominal surgery have a poorer quality of recovery and higher risk of complications, leading to poor disability-free survival when compared with patients without postoperative anaemia.

STUDY DESIGN

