Secondary endpoints include an *a priori* composite of 30-day mortality or major septic complications (sepsis, surgical site infection, anastomotic leak, and pneumonia), plus each individually, acute kidney injury, ICU and hospital stay, unplanned admission to ICU, hospital readmission and quality of recovery (QoR-15).³⁰ We used the following definitions:

1. Death: all-cause mortality at 90 days, then up to 12 months after surgery
2. A composite (pooled) and individual septic complications: sepsis, surgical site infection, anastomotic leak, and pneumonia. [Detailed clinical definitions are provided in the Protocol]
3. Sepsis: using Centers for Disease Control and Prevention (CDC) with National Healthcare Safety Network (NHSN) criteria³⁴
4. Surgical site infection: using CDC criteria³⁴
5. Pneumonia: The presence of new and/or progressive pulmonary infiltrates on chest radiograph plus two or more of the following:
 - i. Fever $\geq 38.5^{\circ}\text{C}$ or postoperative hypothermia $<36^{\circ}\text{C}$
 - ii. Leucocytosis $\geq 12,000 \text{ WBC}/\text{mm}^3$ or leucopenia $< 4,000 \text{ WBC}/\text{mm}^3$
 - iii. Purulent sputum and/or
 - iv. New onset or worsening cough or dyspnoea.
6. Anastomotic leak: A defect of the intestinal wall at the anastomotic site (including suture and staple lines of neorectal reservoirs) leading to a communication between the intra- an extra luminal compartments.
7. Acute kidney injury: according to The Kidney Disease: Improving Global Outcomes (KDIGO) group criteria, but not urine output – for Stage 2 or worse AKI defined as at least 2-fold increase in creatinine, or estimated GFR decrease $>50\%$ ³⁵.
We will also report renal replacement therapy up to 90 days after surgery
8. Unplanned admission to ICU within 30 days of surgery
9. Total ICU stay: additive, including initial ICU admission and readmission times up to Day 30
10. Hospital stay: additive, from the start (date, time) of surgery until actual hospital discharge , plus readmission(s) up to Day 30
11. Quality of recovery: QoR-15 score³⁰ on Days 3 and 30
12. Hospital re-admission at 3, 6 and 12 months

PROCESS DATA CALCULATIONS

Red cell transfusions will be reported as dichotomous data (yes/no, where yes is any red cell volume $\geq 1 \text{ ml}$) data, and calculated for the intraoperative period plus recovery room (combined), and postoperative Days 1, 2 and 3.

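### Complications that occur before the Day 3 haemoglobin can count as outcomes of Day 3 anaemia (endpoints #2-8, clearest for sepsis), and no planned analysis separates them

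*SAP*

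**What the plan says.** **Exposure.** The SAP's Anaemia Group Definition applies the WHO haemoglobin thresholds "as measured on postoperative Day 3", using the lowest value that day. The population is the RELIEF intention-to-treat set, which is fixed at induction of anaesthesia. The same section adds: "Patients with missing Day 3 haemoglobin data will have these values imputed rather than these patients being excluded (details below". Statistical Analyses makes imputation conditional on evidence that missingness depends on patient characteristics, and puts the relevant outcomes into the imputation models.

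**Outcomes.** Under Secondary endpoints the SAP lists a composite that joins death by Day 30 to "major septic complications (sepsis, surgical site infection, anastomotic leak, and pneumonia), plus each individually, acute kidney injury, ICU and hospital stay". Item 8 is "Unplanned admission to ICU within 30 days of surgery", so it runs from surgery. Items 2-7 give no start day. Protocol, Study Procedures, says patients were followed and outcomes recorded daily until discharge.

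**Models.** Endpoints #1-8 and #12 use the primary endpoint's regression. It adjusts for randomised arm, age, sex, ASA status, Charlson score, aspirin, baseline haemoglobin, surgery type, planned HDU/ICU and duration of surgery. Pre-Day 3 characteristics serve to describe the anaemia groups, to examine missingness and possibly to impute. They do not enter the outcome models.

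**Direction.** The hypothesis reads "Adults with anaemia in the immediate postoperative period following major abdominal surgery have a poorer quality of recovery and higher risk of complications", and goes on to say that this leads to poor disability-free survival. The Background names, among the causes of postoperative anaemia, "excess IV fluids (leading to haemodilution), sepsis, and inadequate nutritional intake after surgery".

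**The concern.** For an outcome to follow an exposure, it must occur after the exposure is fixed. Here the exposure is fixed on Day 3 while the clock for complications appears to start at surgery. A patient who becomes septic on Day 2 and has a low haemoglobin on Day 3 adds an event to the anaemic group, although by the SAP's own account the sepsis may have produced the anaemia.

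The study is framed as an association, but its hypothesis has a direction, and a raised risk ratio for sepsis or the septic composite would be read as support for it. Neither document contains a landmark, a lag, an exclusion of early events, a time-varying exposure or any other sensitivity analysis on timing.

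A related problem concerns patients who died before Day 3. They never had a Day 3 haemoglobin, yet the imputation rule makes no exception for them, and the outcome would help to determine the status they are given. This touches death (#1), the composite with 30-day mortality and, slightly, the primary endpoint.

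**Working it through.** The plan gives no figure on this point to reproduce. The check has a documentary part and an illustrative one.

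**1. Time origin of each endpoint against the Day 3 exposure (SAP, Secondary endpoints)**

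| Endpoint | Time origin | Can an event precede the Day 3 Hb? |
|---|---|---|
| #1 death | surgery | Not with a measured Day 3 Hb; only through an imputed status |
| #2-7 septic complications, AKI | none stated; from surgery is inferred from daily recording and the absence of a cut-off | Yes |
| #8 unplanned ICU admission | surgery | Yes |
| #9-10 ICU and hospital stay | initial ICU admission; start of surgery | Includes time before Day 3 |
| #11 Day 3 QoR-15 | Day 3 | Same day as the exposure |

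The reverse path is stated in the documents for sepsis alone. For the rest of #2-8 it is possible but not stated.

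**2. Illustration of size**

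The documents give none of these inputs, so all are assumed: anaemia prevalence p, total event risk R, fraction f of events before the Day 3 Hb, and odds ratio OR between an early event and Day 3 anaemia. Anaemia has no effect on events after Day 3.

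- Early risk: e = R × f.
- a1 = P(anaemia | early event) and a0 = P(anaemia | no early event) solve e·a1 + (1 − e)·a0 = p with odds(a1) = OR × odds(a0).
- Early risk by group: eA = e·a1/p and eN = e·(1 − a1)/(1 − p).
- Later risk, equal in both groups: L = (R − e)/(1 − e).
- From-surgery RR = [eA + (1 − eA)L] / [eN + (1 − eN)L].

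Worked case, p = 0.70, R = 0.10, f = 0.20, OR = 2:

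- e = 0.02, a0 = 0.6975, a1 = 0.8218.
- eA = 0.02 × 0.8218/0.70 = 0.0235; eN = 0.02 × 0.1782/0.30 = 0.0119.
- L = 0.08/0.98 = 0.0816.
- RR = (0.0235 + 0.9765 × 0.0816)/(0.0119 + 0.9881 × 0.0816) = 0.1032/0.0925 = 1.115 (from unrounded values).

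Among patients free of the event at the end of Day 3, both groups have risk L, so the landmark RR is 1.00.

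From-surgery RR at p = 0.70, R = 0.10:

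| Early fraction | OR 1 | OR 1.5 | OR 2 | OR 3 |
|---|---|---|---|---|
| 2% | 1.00 | 1.01 | 1.01 | 1.02 |
| 10% | 1.00 | 1.03 | 1.06 | 1.08 |
| 20% | 1.00 | 1.07 | 1.12 | 1.17 |
| 40% | 1.00 | 1.15 | 1.25 | 1.39 |

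Varying R over 5-20% and p over 50-90%, with 10-40% early and OR 1.5-3, gives 1.03-1.47.

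The formula uses only the joint distribution of early event and anaemia, so it gives the same RR whichever came first. A simulation of 6 million patients with the worked-case inputs agrees. Event before anaemia gave 1.113 from surgery and 1.000 at the landmark; early low Hb before the event gave 1.114 and 0.998.

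**3. Deaths before Day 3 and the primary endpoint**

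Suppose 0.1-0.5% die before Day 3 (3-15 of 3,000), primary risk is 10-20%, p = 0.70 and OR is 1.5-3. The same formula gives an RR of 1.00-1.04.

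**4. Precision of a landmark**

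Take N = 3,000 (Protocol, Statistical Analysis), split 2,100/900 by the assumed 70%. The SE of log RR is √[(1 − rA)/(nA·rA) + (1 − rN)/(nN·rN)], where r and n are the risk and number in each group.

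- From surgery at OR 1: √(0.9/210 + 0.9/90) = 0.1195, a 95% CI factor of exp(1.96 × 0.1195) = 1.26.
- Landmark at f = 20%, OR 1: numbers 2,058 and 882, risk 0.0816, SE 0.135. The ratio is 1.13.
- From OR 3 to OR 1, the SE rises by 4-6% (10% early), 8-13% (20%) and 20-32% (40%).

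**The case against.** The strongest reply is that the order of early events is unclear in both directions. The hypothesis concerns the immediate postoperative period, and the SAP's Background says "A nadir in Hb concentration is most often observed within the first" three to four days. An early complication may therefore follow an early low haemoglobin that the Day 3 value merely reflects. A landmark discards any such effect and answers a narrower question. The study also calls itself an association study, and it adjusts for baseline haemoglobin and operative factors, which the unadjusted illustration does not. All of this stands. It makes the landmark a companion to the planned analysis, not a replacement or a condition for interpreting it.

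Four stronger readings are tempting but unsupported:

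- A reader might infer that all of #1-10 are open to reversal. Death is not, because anyone with a measured Day 3 haemoglobin was alive on Day 3.
- A reader might infer that no rule covers deaths before Day 3. One does: patients with a missing value are kept and imputed. The fault is that it makes no exception for patients who could not have had the value.
- A reader might want the clock for stay reset too, since item 9 is "Total ICU stay: additive, including initial ICU admission and readmission times up to Day 30". No bias has been quantified there. In an accelerated failure time model, removing three days from each group changes the ratio mechanically: assumed medians of 7 and 6 days give 7/6 = 1.17, but 4/3 = 1.33 from Day 3.
- A reader might take a landmark RR near 1 as proof of reverse causation. It only leaves the early order open.

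**Conclusion.** The gap is real and confined to secondary endpoints #2-8. As written, the plan can count events that precede the exposure as its outcomes, and it has no analysis that shows how much of an association comes from them. Sepsis, alone and within the composite, is the one case with a reverse path in the documents.

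Confidence is high that the step is missing and low about its size, because prevalence, event risk, early fraction and odds ratio are all assumed. At 10% early events the distortion (1.03-1.08) is small beside a 95% CI factor of 1.26. At 40% early and OR 3 (1.39) it exceeds that factor. It is nil for any endpoint whose early events are unrelated to Day 3 haemoglobin.

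The imputed status of early deaths is a separate, smaller fault. It reaches #1, the mortality composite and, by at most about 4% under the assumptions shown, the primary endpoint. Nothing here supports the inference that the primary result is compromised. Day 30 QoR-15 and readmission (#12) are largely unaffected.

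**What to change.** 1. Keep the planned from-surgery analyses. Add a prespecified Day 3 landmark sensitivity analysis for #2-8 where onset dates exist: patients alive and free of the given endpoint at the end of Day 3, with later onsets only. Report it beside the main result.
2. Where onset is undated, and for #9-10 and Day 3 QoR-15, describe the result as an association without temporal order. Do not reset the clock for stay.
3. Do not impute Day 3 anaemia for patients who died before Day 3. Report their number and outcomes separately, and state that the anaemia comparison is among patients alive at Day 3. This is a small change to the stated intention-to-treat population and should be acknowledged as one.
4. Optional and minor: define the exploratory transfusion subgroup by transfusion before Day 3. It has no window now, and the SAP already calculates transfusion by period.

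**Cost.** SAP wording and programming on data already held. Onset dates must first be confirmed, since daily recording does not guarantee them. Standard errors rise by about 4-6%, 8-13% or 20-32% if 10%, 20% or 40% of events are early. The landmark excludes any effect of low haemoglobin before Day 3, and the report should say so.
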